3.5 COST AND COMPENSATION

3.5.1 Costs

NIH does not bill health insurance companies or participants for any research or related clinical care that participants receive at the NIH Clinical Center. However, subjects on this study are required to provide the required internet access and may in some cases incur additional charges from their providers.

3.5.2 Compensation

Participants will not be compensated on this study.

3.5.3 Reimbursement

Participants will not be reimbursed on this study.

3.6 OFF-STUDY CRITERIA

- Completion of treatment and follow up
- Participant noncompliance
- Participant requests to be withdrawn from the study
- Lost to follow-up
- Death
- PI decision to close the study
- Permanent loss of ability to consent

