3.6.1 Lost to Follow-up

A participant will be considered lost to follow-up if he or she is unable to be contacted by the study site staff.

The following actions must be taken if a participant fails to participate in a required CALM session:

- Research staff will attempt to contact the participant and reschedule the missed session within 14 days of the originally scheduled time and counsel the participant on the importance of maintaining the assigned session and ascertain if the participant wishes to and/or should continue in the study.
- Before a participant is deemed lost to follow-up, the investigator or designee will make every effort to regain contact with the participant (where possible, 3 telephone calls and, if necessary, an email will be sent to the participant). These contact attempts should be documented in the participant's medical record or study file.
- Should the participant continue to be unreachable, he or she will be considered to have withdrawn from the study with a primary reason of loss to follow-up.

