6 DATA COLLECTION AND EVALUATION

6.1 DATA COLLECTION

The PI will be responsible for overseeing the entry of data into a 21 CFR Part 11-compliant data capture system provided by the NCI CCR and for ensuring data accuracy, consistency, and timeliness. The principal investigator, associate investigators/research nurses, and/or a contracted data manager will assist with the data management efforts. Primary and final analyzed data will have identifiers so that research data can be attributed to an individual human subject participant.

Participant's disease status at the time of study entry will be identified in the database as 1) newly diagnosed or 2) currently recurrent or 3) on surveillance.

Should a participant withdraw from the study, it will be confirmed if they wish to withdraw from 1) all components of the study; 2) completing questionnaires but wish to continue therapy sessions; 3) therapy sessions, but willing to complete questionnaires.

All psychiatric adverse events regardless of severity will be followed until return to baseline or stabilization of event.

Document AEs from the first study intervention, baseline evaluations through study participation.

End of study procedures: Data will be stored according to HHS, FDA regulations, and NIH Intramural Records Retention Schedule as applicable.

Loss or destruction of data: Should we become aware that a major breach in our plan to protect subject confidentiality and trial data has occurred, this will be reported expeditiously per requirements in section [7.2.1](#).

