8.2 SAMPLE SIZE DETERMINATION

The primary objective of this study is to demonstrate the reduction of depressive symptoms from baseline to 6 months using CALM in PCNST participants. Based on the previous study, we expect a mean difference reduction in depressive symptoms of 1.8 with a standard deviation of the difference of 5.7. To detect this difference, we need 80 participants using a 2-tailed test at 5 significance level and 80% power. To account for estimated attrition of 20%, recruitment of 100 participants to have 80 evaluable participants.

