8.3 STATISTICAL ANALYSIS

8.3.1 Analysis of the Primary Endpoint

To demonstrate the effect of CALM on depressive symptoms using PROMIS-Depression, we will perform a paired t-test from baseline to 6 months using a 2-tailed test at a 5% significance level. One interim analysis is planned when half of the participants have undergone CALM treatment. The study will be stopped early if the absolute nominal statistic for paired differences in depressive symptoms is larger than 2.782 (alpha=.0054) to claim the benefit of CALM. At the end of the study, CALM treatment will be claimed to be a success if the absolute nominal critical point is larger than 1.967 (alpha=.0492). The stopping boundary is based on the O'Brien-Fleming method with 2 interim analyses.

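### Removal for undefined noncompliance, or loss of contact after a missed session, ends study participation with no provision for month-6 PROMIS, so the paired primary analysis drops these participants

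*Combined protocol and SAP*

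**What the plan says.** Section 3.6 lists "Participant noncompliance" and loss to follow-up among the reasons for going off study. Noncompliance is not defined there or elsewhere. The only operational use of compliance, in 8.3.2, refers to completing the outcome measures.

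Section 3.6.1 starts from a missed required CALM session. Staff try to reschedule and to regain contact. If the participant remains unreachable, "he or she will be considered to have withdrawn from the study with a primary reason of loss to follow-up". If the participant is reached, the question put is about continuing in the study, and it covers both what the participant wishes and whether he or she should continue.

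Section 6.1 has a more graded rule: "Should a participant withdraw from the study, it will be confirmed if they wish to withdraw from" everything, questionnaires only, or therapy only while still answering questionnaires.

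For the primary endpoint, 8.3.1 states: "we will perform a paired t-test from baseline to 6 months using a 2-tailed test at a 5% significance level". Section 8.2 plans on this basis: "To account for estimated attrition of 20%, recruitment of 100 participants to have 80 evaluable participants". The 20% is not split by reason. No definition of evaluable and no missing-data method is given for the primary endpoint.

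**The concern.** A paired test uses only people with both scores. In a single-arm study there is no control group in which similar losses could offset the effect of selective loss, so who supplies a month-6 score directly shapes the estimate. If exit rules tied to session attendance or compliance also end outcome collection, the analysed set is partly selected on engagement.

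The protocol itself gives reasons to think such people may differ on the outcome. Section 1.2.1 links depressive symptoms to noncompliance with medical treatment, and 3.1 says the outcomes are affected by recurrence. The same pairs drive the early-stopping rule and the final success claim in 8.3.1, and 1.2.2 intends the results to inform the size of a later randomized trial.

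**Working it through.** **The plan's own figure.** Inputs from 8.2: "we expect a mean difference reduction in depressive symptoms of 1.8 with a standard deviation of the difference of 5.7", and "we need 80 participants using a 2-tailed test at 5 significance level and 80% power".

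- Normal approximation: n = ((1.960 + 0.842) × 5.7 / 1.8)² = 78.7, so 79. The noncentral t gives 81. The stated 80 is reproduced within rounding; power at 80 is 79.7%.
- Inflation: 80 / (1 − 0.20) = 100.

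There is no arithmetic error. The inflation protects the number of pairs. It does not protect against selective loss.

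**What happens to month-6 PROMIS by route of exit.**

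- Withdraws from therapy and can be asked: 6.1 offers continued questionnaires, so the score can be kept.
- Stops after the third session: 2.1.1 refers to only 3 required sessions, and nothing takes this person off study, so the score is still sought.
- Removed by the team for noncompliance: off study under 3.6. Section 6.1 is silent on this case.
- Unreachable after a missed required session: deemed withdrawn from the study under 3.6.1. The 6.1 question cannot be put.
- Death or permanent loss of capacity to consent: no score can be recovered.

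The gap is in the third and fourth routes. Loss of the month-6 score there is strongly implied by off-study status but not stated in words. Section 2.3 already distinguishes being off protocol therapy from being off study, but 3.6 gives criteria only for the latter.

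**Size if all 20% is assigned to these exits.** Let p be the share lost. Completer mean − all-enrolled mean = p × (completer mean − leaver mean). With p = 0.20 and completers at −1.8:

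- Leavers unchanged: 0.8 × (−1.8) + 0.2 × 0 = −1.44. Gap 0.36; 1.8 / 1.44 = 1.25, so 25% too large.
- Leavers worsen by 1.8: 0.8 × (−1.8) + 0.2 × 1.8 = −1.08. Gap 0.72; 1.8 / 1.08 = 1.67, so 67% too large.

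**Effect on the test, same assignment.** Suppose the true all-enrolled change is zero. Leavers worsening by D then imply a completer mean of −0.2 × D / 0.8. For D = 1.8 this is −0.45, and for D = 3.6 it is −0.90. With 80 pairs, SD 5.7 and the final nominal alpha of .0492, the test rejects in about 11% and 28% of trials, against 4.9%. This treats the final test alone.

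**A smaller case.** Assume 5 extra scores could be recovered, added to 80 completers:

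- No change in the 5: (80 × −1.8 + 5 × 0) / 85 = −1.69; 1.8 / 1.69 = 1.06, about 6% too large.
- Worsening by 1.8: (80 × −1.8 + 5 × 1.8) / 85 = −1.59; 1.8 / 1.59 = 1.13, about 13% too large.

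The leavers' change scores and the count of 5 are assumptions. The documents give neither.

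**The case against.** A reader might infer that 3.6 and 6.1 contradict each other. They do not: one lists reasons for leaving the study, the other says what is asked when a participant withdraws. What remains is silence about people who are removed or cannot be asked.

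A reader might also infer that the primary analysis keeps mainly those who stayed in therapy. The text does not support that. Noncompliance is not defined as missed sessions. Following 8.3.2 it could mean unreturned questionnaires, in which case the score is already missing and the rule adds little. Participants who leave therapy but can be reached have a route that keeps their questionnaires, and stopping after session 3 triggers nothing.

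For the unreachable, much of the loss comes from being unreachable. Section 3.6.1 already asks for rescheduling within 14 days, three calls where possible and, if necessary, an email, and survey reminders use the same channels. This stands in large part. Still, someone who does not respond after an early missed session may answer a link at month 6, and 3.2 delivers questionnaires by link, apart from the sessions.

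Nor is bias toward benefit established. No outcomes for leavers are given, and 1.2.2 and 3.1 offer extra sessions to those still struggling, so longer engagement can also mark worse mood.

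Finally, the 20% also has to cover death, incapacity and participant request. Entry requires only 3 months' life expectancy against a 6-month endpoint, so those reasons could be a material share, and no change to the exit rules would recover those scores.

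**Conclusion.** The point holds as a gap in outcome collection. As written, the plan makes no provision for month-6 PROMIS after team removal for noncompliance or after a missed-session loss of contact, and the paired t-test then leaves these people out. This can bias the single-arm change if they differ from completers.

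The direction and size are not known from the documents. The 25% and 67% figures are upper illustrations in that they give these exits the whole 20% attrition; they should not be read as an expected bias. The 6% and 13% figures show how much smaller the effect is if only 5 scores are at stake. All four rest on assumed outcomes for leavers. The share of attrition due to these exits cannot be derived.

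The change is worth making because it is cheap and reduces avoidable selective loss in the primary analysis. The absence of a missing-data method for the primary endpoint is a related but separate matter.

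**What to change.** Reconcile 3.6, 3.6.1 and 6.1:

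- Define noncompliance, stating whether it refers to sessions, questionnaires or both.
- Separate the end of therapy sessions from the end of outcome collection, whoever initiates the exit.
- Keep sending the month-3 and month-6 survey links, with the reminders already in 3.2, including after team removal or loss of contact over sessions. Stop only if the participant withdraws from questionnaires, dies or permanently loses capacity to consent.
- State in 8.3.1 that every month-6 score obtained enters the primary analysis regardless of sessions attended. Nothing now excludes such scores, but evaluable is undefined, so this should be written down.

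The cost is a small amendment and a few extra links and reminders, with no added visits. Recovery among the unreachable will be limited. The change concerns data collection only and says nothing about when therapy should stop.

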3.6.1 Lost to Follow-up

A participant will be considered lost to follow-up if he or she is unable to be contacted by the study site staff.

The following actions must be taken if a participant fails to participate in a required CALM session:

- Research staff will attempt to contact the participant and reschedule the missed session within 14 days of the originally scheduled time and counsel the participant on the importance of maintaining the assigned session and ascertain if the participant wishes to and/or should continue in the study.
- Before a participant is deemed lost to follow-up, the investigator or designee will make every effort to regain contact with the participant (where possible, 3 telephone calls and, if necessary, an email will be sent to the participant). These contact attempts should be documented in the participant's medical record or study file.
- Should the participant continue to be unreachable, he or she will be considered to have withdrawn from the study with a primary reason of loss to follow-up.

4 CONCOMITANT MEDICATIONS/MEASURES

No restrictions on participant's current medication.

5 BIOSPECIMEN COLLECTION

N/A

6 DATA COLLECTION AND EVALUATION

6.1 DATA COLLECTION

The PI will be responsible for overseeing the entry of data into a 21 CFR Part 11-compliant data capture system provided by the NCI CCR and for ensuring data accuracy, consistency, and timeliness. The principal investigator, associate investigators/research nurses, and/or a contracted data manager will assist with the data management efforts. Primary and final analyzed data will have identifiers so that research data can be attributed to an individual human subject participant.

Participant's disease status at the time of study entry will be identified in the database as 1) newly diagnosed or 2) currently recurrent or 3) on surveillance.

Should a participant withdraw from the study, it will be confirmed if they wish to withdraw from 1) all components of the study; 2) completing questionnaires but wish to continue therapy sessions; 3) therapy sessions, but willing to complete questionnaires.

All psychiatric adverse events regardless of severity will be followed until return to baseline or stabilization of event.

Document AEs from the first study intervention, baseline evaluations through study participation.

End of study procedures: Data will be stored according to HHS, FDA regulations, and NIH Intramural Records Retention Schedule as applicable.

Loss or destruction of data: Should we become aware that a major breach in our plan to protect subject confidentiality and trial data has occurred, this will be reported expeditiously per requirements in section [7.2.1](#).

6.2 DATA SHARING PLANS

6.2.1 Human Data Sharing Plan

The PI will share coded linked human data generated in this research for future research

- in an NIH-funded or approved public repository clinicaltrials.gov
- in BTRIS
- in publication and/or public presentations

at the time of publication or shortly thereafter.

6.2.2 Genomic Data Sharing Plan

Genomic Data Sharing Policy is non-applicable for this protocol as no genomic data are analyzed.

6.3 TOXICITY CRITERIA

The following adverse event management guidelines are intended to ensure the safety of each participant while on the study. The descriptions and grading scales found in the revised NCI Common Terminology Criteria for Adverse Events (CTCAE) version 5.0 will be utilized for AE reporting. All appropriate treatment areas should have access to a copy of the CTCAE version 5.0.

A copy of the CTCAE version 5.0 can be downloaded from the CTEP web site (http://ctep.cancer.gov/protocolDevelopment/electronic_applications/ctc.htm).

7 NIH REPORTING REQUIREMENTS / DATA AND SAFETY MONITORING PLAN

7.1 DEFINITIONS

Please refer to definitions provided in Policy 801: Reporting Research Events found at: <https://irbo.nih.gov/confluence/pages/viewpage.action?pageId=36241835#Policies&Guidance-800Series-ComplianceandResearchEventReportingRequirements>.

7.2 OHSRP OFFICE OF COMPLIANCE AND TRAINING / IRB REPORTING

7.2.1 Expedited Reporting

Please refer to the reporting requirements in Policy 801: Reporting Research Events and Policy 802 Non-Compliance Human Subjects Research found at: <https://irbo.nih.gov/confluence/pages/viewpage.action?pageId=36241835#Policies&Guidance-800Series-ComplianceandResearchEventReportingRequirements>.

7.2.2 IRB Requirements for PI Reporting at Continuing Review

Please refer to the reporting requirements in Policy 801: Reporting Research Events found at: <https://irbo.nih.gov/confluence/pages/viewpage.action?pageId=36241835#Policies&Guidance-800Series-ComplianceandResearchEventReportingRequirements>.

7.3 NCI CLINICAL DIRECTOR REPORTING

Problems expeditiously reviewed by the OHSRP in the NIH eIRB system will also be reported to the NCI Clinical Director/designee; therefore, a separate submission for these reports is not necessary.

7.4 NIH REQUIRED DATA AND SAFETY MONITORING PLAN

The clinical research team will meet on a weekly basis when participants are being actively treated on the trial to discuss each participant.

All data will be collected in a timely manner and reviewed by the principal investigator or a lead associate investigator. Events meeting requirements for expedited reporting as described in section **7.2.1** will be submitted within the appropriate timelines.

The principal investigator will review adverse event and response data on each participant to ensure safety and data accuracy. The principal investigator will personally conduct or supervise the investigation and provide appropriate delegation of responsibilities to other members of the research staff.

8 STATISTICAL CONSIDERATIONS

8.1 STATISTICAL HYPOTHESIS

Primary Endpoint:

- To demonstrate the effects of the CALM intervention in the reduction of depressive symptoms using the PROMIS-Depression scale in PCNST participants from baseline to 6 months.

Secondary Endpoints:

- To demonstrate the short-term effects of the CALM intervention in the reduction of depressive symptoms using the PROMIS-Depression scale in PCNST participants from baseline to 3 months.
- To determine the effects of the CALM intervention on death anxiety using the Death and Dying Distress Scale at both 3 and 6 months, compared to baseline.
- To describe the feasibility of implementing CALM remotely in a sample of PCNST participants.

Exploratory Objectives:

- To determine the effects of the CALM intervention on psychological well-being as measured by the Quality of Life Cancer Scale (QUAL-EC) and the modified brief Experiences in Close Relationships (ECR-M-16) questionnaire at both 3 and 6 months, compared to baseline
- To explore the effects of the CALM intervention, more specifically the relationship between distress and symptom burden as measured by the M.D. Anderson Symptom Inventory-Brain tumor (MDASI-BT) or M.D. Anderson Symptom Inventory-Spine Tumor (MDASI-SP) symptom severity and symptom factor scores.
- To explore the effects of the CALM intervention on the relationship between distress and symptom interference as measured by the MDASI-BT or MDASI-SP interference scores.

To explore the effects of the CALM intervention on health status as measured by the EQ-5D and CEQ.

8.2 SAMPLE SIZE DETERMINATION

The primary objective of this study is to demonstrate the reduction of depressive symptoms from baseline to 6 months using CALM in PCNST participants. Based on the previous study, we expect a mean difference reduction in depressive symptoms of 1.8 with a standard deviation of the difference of 5.7. To detect this difference, we need 80 participants using a 2-tailed test at 5 significance level and 80% power. To account for estimated attrition of 20%, recruitment of 100 participants to have 80 evaluable participants.

8.3 STATISTICAL ANALYSIS

8.3.1 Analysis of the Primary Endpoint

To demonstrate the effect of CALM on depressive symptoms using PROMIS-Depression, we will perform a paired t-test from baseline to 6 months using a 2-tailed test at a 5% significance level. One interim analysis is planned when half of the participants have undergone CALM treatment. The study will be stopped early if the absolute nominal statistic for paired differences in depressive symptoms is larger than 2.782 (alpha=.0054) to claim the benefit of CALM. At the end of the study, CALM treatment will be claimed to be a success if the absolute nominal critical point is larger than 1.967 (alpha=.0492). The stopping boundary is based on the O'Brien-Fleming method with 2 interim analyses.

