Understanding the effects of CALM using telepsychology in this patient population will help in identifying feasible methods in treating patients' distress and will be used to calculate sample size and effect for a multicenter randomized study, evaluating CALM versus standard of care in the PCNST patient population. This can allow for more tailored psychosocial interventions focused on patients' needs and can provide additional coping mechanisms utilized throughout the illness trajectory in dealing with challenges associated with a PCNST diagnosis.

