To evaluate the feasibility of implementing CALM remotely, we will use descriptive statistics to summarize information, including rates of compliance and attrition, and participant satisfaction. This will be evaluated at the interim analysis using the same percentages outlined for the final analysis. The quantity of missing data, the variability of the data over time, and trends over time will be especially important to report to assess the feasibility of CALM. We will report participant satisfaction with the CALM experience using the responses from the WIWI instrument and thematic analysis of participant responses from the interviews. Participant's responses will go through a multi-stage process of categorizing and coding to identify themes associated with the participants experience with the CALM intervention. Results of the analysis will be reported out separately.

We will consider the study to be feasible if the following criteria are met:

- Accrual: Recruitment of 100 participants to have 80 evaluable participants in two years and less than 20% of eligible participants unable to participate due to lack of electronic devices (computer, smartphone, or iPad).
- Compliance: at least 80% of participants completing the outcome measures at all time points

Tolerability and acceptability will be assessed through the WIWI.

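### If the trial stops early for efficacy, the plan provides neither an adjusted estimate for sizing the randomized trial nor a reading of the accrual criterion

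*Combined protocol and SAP*

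**What the plan says.** Section 8.3.1 tests the change in PROMIS-Depression from baseline to 6 months with a paired t-test. On the interim it says "One interim analysis is planned when half of the participants have undergone CALM treatment". The consequence of crossing the limit is not discretionary: "The study will be stopped early if the absolute nominal statistic for paired differences in depressive symptoms is larger than 2.782". Section 10.1 also lists demonstrated efficacy among the grounds for ending the study.

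Two other places depend on what happens next. At the end of section 1.2.2, the findings "will be used to calculate sample size and effect for a multicenter randomized study". In section 8.3.2, one of the conditions for calling the study feasible is "Recruitment of 100 participants to have 80 evaluable participants in two years". The same section says feasibility will be looked at during the interim using the percentages set for the final analysis.

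The plan does not say whether enrolment continues while the interim data mature, whether participants already enrolled at a stop complete month 6 and are counted, whether the estimate is adjusted for the stopping rule, or how the accrual count is read after a stop.

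**The concern.** A trial that stops because its interim result was large is selected for overestimation. Here the estimate has a declared second use, as the effect on which a randomized trial is sized. If the unadjusted stopped estimate is used for that, the later trial will tend to be too small.

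The accrual criterion raises a separate problem. It is a count, 100 enrolled to give 80 evaluable, and a study halted on its interim result will usually not reach it. Early success on the primary endpoint would then be recorded as a failure of accrual, although accrual may have been on schedule.

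**Working it through.** **Inputs.** Section 8.2: "we expect a mean difference reduction in depressive symptoms of 1.8 with a standard deviation of the difference of 5.7"; a two-sided 5% test with 80% power on 80 evaluable, and 100 enrolled because 20% are expected to drop out. Section 8.3.1: interim limit 2.782 (nominal p .0054), final limit 1.967 (nominal p .0492). Section 8.3.2: 100 enrolled in two years. I take one interim look and one final look.

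**The plan's own figures.** n = (5.7 × (1.960 + 0.842) / 1.8)² = 78.7, so 79 by the normal formula and 81 by the exact t calculation. Power at 80 is 79.7% (t) or 80.6% (normal). 80 / 0.8 = 100. The stated 80 and 100 reproduce, and both nominal p-values match their limits.

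**Chance of stopping, and the estimate given a stop.** Section 8.3.1 does not say whether half means 40 or 50 pairs, so both are shown.

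- With 40 pairs, SE = 5.7/√40 = 0.901. At a sample SD of 5.7, the smallest mean reduction that stops the trial is 2.782 × 0.901 = 2.51, or 39% above 1.8.
- Treating the SD as known: P(stop) = 1 − Φ(2.782 − 1.8/0.901) = 0.22. The mean given a stop is 1.8 + 0.901 × φ(0.785)/0.2163 = 3.02.
- Simulating the two-look paired t design (200,000 trials, SD estimated): P(stop) = 0.23 and the mean given a stop is 2.93, which is 2.93/1.8 = 1.63 times the truth. This is lower than 3.02 because a low sample SD lets smaller means cross. The standardised effect averages 0.54 against a true 0.32.
- With 50 pairs, simulated: P(stop) = 0.305 and the mean given a stop is 2.69 (+50%).
- Other true values, 40 pairs: at 1.0, P(stop) = 0.06 and mean given a stop 2.72; at 2.5, 0.51 and 3.18.

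**Averaged over all trials (40 of 80).** Trials that continue average 1.63. Overall: 0.231 × 2.93 + 0.769 × 1.63 = 1.93, or +7%.

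**Illustration for the randomized trial.** Assume SD 5.7 in each arm and no change under usual care; the documents give neither figure. With a two-sample t-test at two-sided 5% and 80% power, sizing on 2.93 gives 61 per arm, and sizing on 1.8 gives 159. With 61 per arm and a true difference of 1.8, power is about 41%. Sizing on 2.69 gives about 71 per arm and about 47%.

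**Accrual after a stop.** Assume even accrual of 100/24 = 4.17 per month, continuing until month-6 data are in. The last column allows for the two-week visit window.

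| Half means | Month-6 data complete | Enrolled by then | Enrolments saved |
|---|---|---|---|
| 40 enrolled | 9.6 + 6 = 15.6 | 65 | 33–35 |
| 50 enrolled (40 evaluable at 20% attrition) | 12 + 6 = 18 | 75 | 23–25 |
| 50 completers (62.5 enrolled) | 15 + 6 = 21 | 87.5 | 10–12 |

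If enrolment pauses at 50, the saving is 50. In the central case, 75 × 0.8 = 60 evaluable, short of 80. For 100 to be enrolled when the 50th participant reaches month 6, accrual would have to be 50/6 = 8.3 per month, twice the planned rate.

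**Effect of following everyone already enrolled.** With 60 evaluable, the mean after crossing is (40 × 2.93 + 20 × 1.8)/60 = 2.55, still 42% too large.

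**The case against.** An O'Brien–Fleming efficacy stop is a recognised choice. The primary objective is to demonstrate a reduction, and sizing a later trial is one downstream use. At the design effect about 77% of trials do not stop, and those estimates run slightly low. Some selection exists without any interim: among fixed 80-pair trials that reach significance, the estimate averages about 2.02 (+12%). A single-arm change from baseline is not a between-arm effect, so it could mislead the randomized trial whether or not this one stops. Stopping can also spare questionnaire burden and bring the randomized trial forward. All of this stands. It limits the point to the stopped branch, but in that branch the sponsor holds only the stopped estimate.

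A reader might infer three stronger things.

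- That the efficacy and feasibility rules contradict each other. They answer different questions, and the percentage criteria are explicitly judged at the interim. Only the count of 100 and 80 lacks an interim reading.
- That a stop saves few participants, since nobody is spared an inferior arm. The documents do not fix the saving: it runs from about 10 to 50 of 100, depending on what half means and whether enrolment pauses.
- That the stop should therefore be removed. This is a trade-off. Announcing efficacy while continuing to enrol in an open, self-reported study could raise expectations and distort later responses.

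**Conclusion.** The concern holds, conditionally. At the plan's assumed effect there is roughly a one-in-four chance (23% with 40 pairs, 30% with 50) of ending with an unadjusted estimate that averages 50–63% too large. The average bias of about 7% is small, but it does not describe a trial that has stopped. The documents do not support saying that the follow-on trial will be underpowered. That needs a stop, use of the unadjusted estimate, and the illustrative assumptions on SD and usual care behind the 41%.

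The accrual part is a feasibility rule that misfires. After a stop the count generally cannot be met unless accrual runs at about twice the planned rate. This part rests on the assumption of even accrual.

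**What to change.** If the stop is kept, add to sections 8.3.1 and 8.3.2:

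- (a) All participants already enrolled when the limit is crossed complete the month-6 questionnaires and enter the reported estimate. This lowers the bias but does not remove it.
- (b) A named, prespecified estimate that allows for the stopping rule is reported beside the unadjusted one, and is the one used to size the randomized trial. It should address bias given a stop; correcting only the average bias of about 7% would leave most of the problem.
- (c) After an early stop, accrual is judged pro rata against 100 in two years. At month 18 that is 100 × 18/24 = 75 enrolled.

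State also whether half means 40 evaluable, 50 enrolled or 50 completers, and whether enrolment pauses for the interim.

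The cost is a protocol amendment with IRB approval, a little more analysis, and a somewhat later final report. Dropping the efficacy stop and continuing to 100 would also remove the stopping bias and the accrual conflict, and stays within the planned enrolment. That is an option for the sponsor to consider, not a required correction.
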